Baseline assessments of cognitive status and functioning, as well as EEG, will be conducted in weeks 1-2. Time commitment for baseline assessments is approximately 4-5 hours. Participants will then be assigned to (a) active training or (b) no training conditions in a pseudo-random order, matched across key demographic variables. The no training condition will serve to assess changes to EEG and other measurements with repeated testing in the absence of active training. This will lay a foundation for future studies that will incorporate an active comparison intervention.

Participants in active training will complete seven training sessions in weeks 3-10. Training sessions last 2 hours, and participants are requested to complete approximately 2.5 hours of additional skill practice over the course of each week outside of session (total  $\sim 4.5$  hours per week). The same overall training time will be targeted ( $\sim 32$  hours) for all individuals, although the training schedule will accommodate variations in individuals' schedules and availability over the course of  $\sim 8$ -10 weeks to maximize engagement. In the 2 weeks after training concludes, participants will complete a second round of assessments ( $\sim 3$ -4 hrs). Participants will be compensated \$20/hr for their time during the assessment portions of the study as well as for their travel expenses at \$0.55/mile for travel greater than 20 miles to and from the study site.

Enrollment will begin within 3 months of the initiation of the grant period, and continue through month 21. Data will be checked and pre-processed on a rolling basis and final analyses and reports will be completed in months 22-24.

**Training Intervention:** Training follows a manualized protocol, with seven in-person two-hour sessions (Loya et al., 2014; Rodriguez et al., 2014) and instructions to practice skill use while playing the Startup-to-CEO game for 30 minutes/day, five times per week, and to practice skill use within the context of their daily life. Game scenarios are utilized to highlight contexts where goal-directed functioning is susceptible to disruption and where skill use might be helpful. They further help facilitate discussions about skill application in personal life. In addition, twice weekly semi-structured phone check-ins are conducted to provide motivational support and reinforce skill use.

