**Pre- and Post-training Assessments of Neuropsychological Performance:** Standardized tests will be administered before and after training (Novakovic-Agopian et al., 2011). The Assessor will be blind to treatment status. All instruments have well-established psychometric properties, and many are included in NINDS Common Data Elements for TBI (indicated with “\*”). Attention and executive function will be assessed using Letter Number Sequencing\* (WAIS-IV); Auditory Consonant Trigrams; Digit Vigilance Test; Design and Verbal Fluency Switching; Trails B\*; DKEFS\* Color-Word Interference: Inhibition and Inhibition/Switching subtests (Delis & Kaplan, 2001). To account for practice effects, alternative test forms will be used when possible, and/or norms for repeated testing will be used. The major outcome measures will be a composite score (averaged z scores) of the attention/executive function domain (Arnemann et al. 2015) and the Automated Operation Span Task, which assesses WM in the presence of distractions (Unsworth et al., 2005). Training effects on primary outcomes will be assessed by computing pre-post change scores. Participants will complete questionnaires of self-perceived changes in cognitive functioning.

**Self-Report Questionnaires:** Each participant will be given two additional questionnaires to assess psychological symptoms as potential covariates. The PCL-5 is a 20-item self-report measure of DSM-5 PTSD symptoms used for screening or monitoring symptoms of PTSD (Weathers, et al., 2013). A *cut-off score of 38 has been recommended as a threshold for diagnosis of PTSD (Weathers et al., 2013)*. The Beck Depression Inventory (BDI) is one of the most commonly used self-reported screens for major depressive disorder. *A cut-off score of 19 has been used as a threshold for major depressive disorder for Veterans with mild TBI history (Homaifar et al., 2009)*. Participant replies will be monitored for suicidal ideation or intent. If there is any indication that a participant is a danger to self or others, a protocol has been established to ensure that he or she will be further evaluated by [name] or [name] to determine what level of intervention is necessary. VANCHCS Mental Health Service provides emergency walk-in evaluations, if it is believed that immediate or a greater level of intervention is necessary. In addition, all participants are provided information about the Suicide Hotline number for Veterans ([name]).

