## Experimental Design

### EEG of Working Memory with and without a secondary attention task

Rationale: Previous studies in this population have shown a decline in WM performance that is exacerbated by increased task demands (Honzel et al., 2014). An established EEG marker of WM retrieval, the ERP old/new effect, indexed this impairment. Another EEG marker, frontal midline theta, is a sensitive correlate of working memory load (Gevins et al., 1997) that exhibits increases in power during cognitive demands for WM (Onton et al., 2005). This experiment will test the hypotheses that (a) patients will show changes in these markers with training; and (b) the EEG changes will explain variability in behavioral changes as measured by the operation span score and the attention/executive function composite score. We will examine EEG and behavioral performance on the Sternberg WM task alone and when the flanker interference task is performed during the maintenance period. Preliminary results from the training intervention suggest that improvements in working memory, attention, and executive functions can occur. Temporally sensitive EEG measures may elucidate the neural correlates of these changes, and help to explain individual differences in treatment response.

Experimental Design: The study will use the methods of Honzel et al. (2014), briefly described below.

Single-Task Condition (Sternberg Memory Task): Participants will be asked to remember either one or four consonants. After an 8500 ms delay, another consonant will be presented (probe). Participants respond with a button press to indicate whether the probe was part of the previous memory set (old) or whether the

probe was not part of the memory set (new).

**Single-Task Condition (Arrow Flanker Task):** Participants will be instructed to respond with a button press to indicate whether the central arrowhead points to the left or the right. Flanking arrows, positioned either above, below, or both above and below the central arrow, can point in either the same (congruent) direction (40% of trials) or different (incongruent) direction (60% of trials). Each flanker stimulus is presented for 200 ms, with the next trial beginning 300 to 500 ms after a response was made.

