**Dual-Task Condition (Sternberg Memory Task + Arrow Flanker):** Participants will be required to perform the arrow flanker task during the delay interval of the Sternberg memory task. Nine flanker trials begin 300 to 500 ms following the presentation of each memory set. The stimulus parameters are the same as for the single-task flanker. The Sternberg probe is then presented 500 ms following the final flanker trial, and participants respond to indicate whether this item was in the previous memory set.

**Statistical Analysis:** The ERP old/new effect will be analyzed using a mixed effects ANOVA controlling for task (single, dual), set size (one, four), and time point (pre, post). The primary neuropsychological outcome measures will be included in the models as appropriate to assess changes from pre- to post-training. To examine the effects of repeated testing, differences in ERP mean amplitudes between patient groups (trained, untrained), task, and set size will be also be tested using a separate mixed effects ANOVA to control for random effects due to subject. Pre/post differences in Sternberg WM accuracy will be tested using a hierarchical generalized linear model. Time-frequency responses will be analyzed with the same mixed and linear models, with separate calculations for each frequency band, and a repeated measures model including all frequency bands.

**Predicted Results:** We predict that Veterans who show cognitive gains with training (based on neuropsychological measures) will show an increase in the ERP old/new effect in the dual task condition. Additionally, as prior work has shown that WM impairment in ADHD is characterized by decreased levels of alpha power during encoding, and compensatory increases in theta during maintenance (Lenartowicz, et al. 2014), we predict that cognitive gains will be reflected by changes in theta and alpha power over frontal scalp. Importantly, we can determine with precise temporal resolution whether the neural manifestations of training improvements occur during WM encoding, maintenance, and/or retrieval. Additional analyses will determine whether these EEG markers can predict which patients will improve with training.

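### The two major behavioural outcomes rest on pre-post change scores; the plan should name a trained-versus-untrained contrast adjusted for baseline score

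*Combined protocol and SAP*

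**What the plan says.** All references are to the combined protocol and SAP.

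- **Pre- and Post-training Assessments of Neuropsychological Performance** names two major outcomes, the attention/executive composite (averaged z scores) and the Automated Operation Span. Its only sentence on their analysis is "Training effects on primary outcomes will be assessed by computing pre-post change scores". On retest gains it says "To account for practice effects, alternative test forms will be used when possible, and/or norms for repeated testing will be used".
- **Self-Report Questionnaires** adds the PCL-5 and BDI "to assess psychological symptoms as potential covariates". The baseline outcome score is not mentioned.
- **Study design and participant flow** places baseline assessment before assignment. Assignment is "in a pseudo-random order, matched across key demographic variables". The role of the untrained arm is given as "The no training condition will serve to assess changes to EEG and other measurements with repeated testing in the absence of active training".
- **Statistical Analysis, under EEG of Working Memory,** says "The primary neuropsychological outcome measures will be included in the models as appropriate", with task, set size and time point as the listed factors. The group comparison follows separately: "differences in ERP mean amplitudes between patient groups (trained, untrained), task, and set size will be also be tested". Time-frequency responses use the same models.
- **The rationale of that experiment** uses behavioural change as something to be explained: "the EEG changes will explain variability in behavioral changes as measured by the operation span score" and the composite. The resting-state section correlates EEG markers with baseline and with change.

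**The concern.** A change score is a derived variable, not a comparison. For the two behavioural outcomes the plan does not say who is compared with whom, by what model, or with which covariates. Two consequences follow.

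**The contrast is not named.** Alternate forms are used only where available, and norms may replace them, so some retest gain may remain. A mean change within the trained arm mixes that gain with the training effect.

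**Baseline is not used.** If the arms are compared on unadjusted change, chance imbalance at baseline adds variance that the baseline score could remove. Under chance imbalance the change-score contrast is unbiased on average, so this loss is one of precision only. It is also conditional, because the text does not exclude adjustment.

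**Working it through.** **The plan's own figure.** Sample Size Calculation gives 13 per group from a difference of 1.097 and a residual error of 0.956. A two-sample t test (noncentral t, two-sided 5% assumed) gives 76.6% power at 12 and 80.1% at 13, so the figure reproduces. It sizes the ERP old/new effect; no power figure is given for the behavioural outcomes.

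**What the group contrast protects against.** Suppose change is tested only within the 20 trained participants by a one-sample t test (df 19, noncentrality = gain × √20), and training has no effect. A pure retest gain of 0.2, 0.3 or 0.5 SD of change (assumed values) would then be significant about 14%, 25% or 56% of the time.

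**What baseline adjustment adds to the contrast.**

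Inputs from the documents: 20 per group, N = 40. No dropout allowance is stated, so 20 analysed per group is assumed. Also assumed: pre/post correlation ρ, post/pre SD ratio s, and baseline SD set to 1.

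- Variance of change: s² + 1 − 2ρs
- Variance after adjustment: s²(1 − ρ²) × f, with f = 1 + 1/(N − 4) = 37/36 = 1.0278 for the estimated slope
- Example, s = 1 and ρ = 0.7: change 2 − 1.4 = 0.600; adjusted 0.51 × 1.0278 = 0.524; ratio 0.874, a saving of 13%

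Ratio of adjusted to change-score variance:

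| ρ | s = 0.9 | s = 1.0 | s = 1.1 |
|---|---|---|---|
| 0.5 | 0.686 | 0.771 | 0.840 |
| 0.7 | 0.772 | 0.874 | 0.947 |
| 0.8 | 0.810 | 0.925 | 0.995 |
| 0.9 | 0.832 | 0.976 | 1.027 |

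Simulation with 60,000 runs per cell agrees to within 0.003. The mean error of both estimators is within 0.002 under chance imbalance.

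The ratio is largest when ρs = 1. The change variance is then s² − 1 and the adjusted variance (s² − 1) × f, so adjustment can cost at most f − 1, about 2.8%. At s = 1 it loses only above ρ = 0.946; at s = 1.1, only between 0.812 and 0.957; at s = 0.9, nowhere.

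**Approximate 95% CI half-width at s = 1**, in baseline-SD units: t × √(variance × 2/20), with df 38 for change and 37 for adjustment.

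| ρ | Change score | Adjusted | Change-score n per group to match (20/ratio) |
|---|---|---|---|
| 0.5 | 0.640 | 0.563 | 25.9 |
| 0.7 | 0.496 | 0.464 | 22.9 |
| 0.9 | 0.286 | 0.283 | 20.5 |

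**Brain-behaviour analyses.** With no training effect, the correlation of change with baseline is (ρs − 1)/√(s² + 1 − 2ρs). At ρ = 0.5, 0.7 and 0.9 this is −0.50, −0.39 and −0.22 for s = 1, and −0.43, −0.28 and −0.02 for s = 1.1. An EEG marker related to baseline score could therefore correlate with change for that reason alone, but how strongly depends on the assumed values.

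**The case against.** The strongest reply is that this is incomplete specification, not a wrong analysis. The untrained arm is there to assess repeated-testing change in measurements beyond EEG, the neuropsychological outcomes enter the models where appropriate, and nothing confines change scores to one arm. A comparison was evidently intended. That stands, but intent does not supply a model, and the one model with a group term is written for other endpoints.

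Second, most of the benefit comes from naming the contrast, while the variance figures measure only what baseline adds once a contrast exists. Those figures rest on assumed correlations and SDs, and at high correlation the gain is negligible. This is true and limits the weight of the point. The worst-case cost is nevertheless small and bounded.

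Third, demographic matching may already shrink baseline imbalance. Suppose it removed 30% of the imbalance variance (assumed). At ρ = 0.7 and s = 1 the change-score variance becomes 0.51 + 0.09 × 0.7 = 0.573, and 0.524/0.573 = 0.915, so the saving falls from about 13% to about 9%. The gain is reduced, not removed.

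Fourth, assignment is pseudo-random. If imbalance is systematic, the adjusted and change-score analyses may estimate different quantities, and neither is then clearly less biased. That stands as a caveat, and it is a reason to fix the model before the data are seen.

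Finally, this is a pilot powered on an ERP measure. That lowers the stakes, although the plan itself calls the behavioural measures primary outcomes.

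**Conclusion.** The concern holds as a cheap improvement. The plan names neither a trained-versus-untrained contrast nor baseline adjustment for its two major behavioural outcomes, and a better analysis is available from data already to be collected. At equal SDs and 20 analysed per group, adjustment saves about 23% of the variance at ρ = 0.5 and 2% at ρ = 0.9. Across the grid examined the result runs from a 31% saving to a 2.7% loss. These sizes depend on correlations and SD ratios that the documents do not give, and on imbalance being due to chance. The case for naming the group contrast does not depend on them. Nothing here invalidates the pilot.

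**What to change.** For each of the two outcomes, pre-specify a regression of post-training score on group and baseline score. Report the adjusted trained-minus-untrained difference with its 95% CI as the training effect, and keep change scores as description. Regressing change on group and baseline gives the same group effect. State in the same place whether the matching variables, PCL-5 and BDI enter the model.

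In the brain-behaviour and resting-state analyses, keep change as the stated outcome and add a sensitivity analysis that includes the baseline score.

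The cost of the main change is one or two sentences of analysis text and one degree of freedom per model, with no new data or visits. Where adjustment does not help, the variance penalty is at most about 2.8%. Because assignment is pseudo-random, the choice of model must be fixed before the data are seen.

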**Pre- and Post-Training EEG:** Participants will attend testing sessions pre- and post-training. The first phase of each session measures several minutes of resting state brainwaves for use in connectivity modeling (Langer et al., 2013). Participants will complete a brief assay of self-regulation, with instructions to relax and focus on the cycle of breathing, re-directing attention if the mind wanders, as in our prior fMRI study (Arnemann et al., 2015). In the second phase, participants will perform our well-validated working memory dual task while EEG is recorded and averaged using standard methods. EEG time-frequency analyses will target the theta and alpha bands based on prior studies (Thornton & Carmody, 2009). This experiment is ideal for use in evaluating potential neural mechanisms of our targeted training, because of its sensitivity to working memory load and distractions. Data will be collected by staff in [name] lab, and EEG analysis carried out by [name], who has experience describing EEG markers and evaluating novel training approaches in clinical populations (Pineda et al., 2014).

**ERP Recording:** Continuous EEG will be recorded from 64 scalp electrodes and two electrodes placed on the left and right mastoids using the ActiveTwo Biosemi electrode system. Four electrodes placed laterally and below both eyes will record blinks and eye movements. The EEG will be sampled at 512 Hz. Biosemi uses a “common mode sense” active electrode and “driven right leg” passive electrode to form a feedback loop that serves as the “ground” electrode. All signals will be recorded using ActiView software.

**ERP Data Analysis:** Off-line analysis will be completed using Brain Vision Analyzer software. Data will be re-referenced to the average of the mastoid electrodes and bandpass filtered from 0.1 to 30 Hz (48 dB/octave). The EEG will be segmented for each trial beginning 100 ms pre-stimulus and extending to 900 ms post-stimulus onset. EEG will be corrected for blinks using the Gratton procedure; artifacts exceeding 150  $\mu$ V will be rejected. Segments will be baseline corrected and averaged with similar trials. ERPs will be

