quantified by computing mean amplitudes in defined latency windows relative to a 100 ms pre-stimulus baseline. The primary measure will be the ERP “old/new effect” elicited during memory retrieval, time-locked to probe onset. This will be quantified by subtracting mean amplitude for Old – New probes (300-500 ms post-stimulus) at midline electrodes (Honzel et al., 2014).

**EEG Time-Frequency and Network Analysis:** Off-line analysis for resting state and dual task data will be performed in the EEGLAB Matlab toolbox (Delorme & Makeig, 2004). Data will be filtered with bandpass limits of 0.1 to 55 Hz using a standard FIR filter and re-referenced to the average of mastoid electrodes. Periodic artifacts, such as eyeblinks, will be removed using the Infomax Independent Component Analysis (ICA) algorithm. Remaining data will be further band filtered into four frequency bands (theta: 4-8 Hz, alpha: 8-13 Hz, beta: 15-30 Hz, & gamma: 30-55 Hz), and power envelope and phase angle will be extracted with a Hilbert transform.

Resting state connectivity will be calculated over two second epochs using a graph theoretical approach comparing each pair of electrodes in each frequency band, based on correlation of band power changes, and degree of phase coherence. *As we are working with resting state data, we have no a priori hypothesis about directionality of information flow. Therefore, correlations of these measures will suffice (Bastos & Schoffelen, 2016), thereby decreasing computation demands.* Spurious connectivity will be corrected by eliminating neighboring electrode connections and ignoring electrode pairs with 0 degrees of phase lag. Remaining electrode pairs will be adjusted to a common threshold to control number of network connections across patients. From these binarized connectivity matrices, modularity and characteristic path length (CPL) will be calculated using the Matlab toolbox, EEGNET (Hassan, et al. 2015). Time-frequency responses to dual task conditions will be calculated using Hilbert transformed data, epoched and averaged over the same time window and baseline as ERP analysis.

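### The correction for spurious resting-state connectivity does not remove instantaneous mixing, so modularity and characteristic path length can partly reflect it

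*Combined protocol and SAP*

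**What the plan says.** The relevant text is in Research Design and Methods, mainly under EEG Time-Frequency and Network Analysis.

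- **Recording.** "Continuous EEG will be recorded from 64 scalp electrodes" and "The EEG will be sampled at 512 Hz" (ERP Recording). For the network analysis, data are "re-referenced to the average of mastoid electrodes". No source-level step is described.
- **Edges.** "Resting state connectivity will be calculated over two second epochs", for every electrode pair in each of four bands, "based on correlation of band power changes, and degree of phase coherence". The plan says "correlations of these measures will suffice" because it has no directional hypothesis and wants to limit computing. Neither reason concerns mixing.
- **Correction.** "Spurious connectivity will be corrected by eliminating neighboring electrode connections and ignoring electrode pairs with 0 degrees of phase lag". The plan gives no tolerance around 0, no rule for 180 degrees and no definition of a neighbour. It does not say whether lag is judged per epoch or over the whole recording, or how the lag rule applies to the band-power network.
- **Other steps.** "Periodic artifacts, such as eyeblinks, will be removed using the Infomax Independent Component Analysis (ICA) algorithm". This is artifact removal and is not presented as a correction for mixing. A common threshold then fixes the number of connections, the matrices are binarized, and modularity and characteristic path length (CPL) are computed.

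Under Resting State EEG and treatment outcome prediction, these metrics enter Spearman screening and stepwise regression as candidate predictors of cognitive gain. The largest differences are expected in theta and alpha.

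**The concern.** The plan recognises that some scalp connections are false, but its rule fails in three ways:

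1. Estimated lags scatter around 0, so a condition of 0 degrees with no tolerance removes almost nothing.
2. A source that reaches two electrodes with opposite sign gives a lag of 180 degrees, which the rule keeps.
3. Mixing raises the band-power correlation of a pair whatever lag is estimated for it.

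The edge count is also fixed, so each dropped pair is replaced by the next strongest, which may itself be a product of mixing.

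What is at stake is the interpretation of the resting-state prediction aim. If some edges reflect head geometry, source orientation or the reference, then an association between modularity or CPL and training response, or its absence, cannot be attributed cleanly to brain network organisation.

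**Working it through.** The plan gives no figure for this rule, so there is none to reproduce. The check is algebra followed by simulation.

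**1. Sign.** Let independent sources k with power P_k reach electrode i with real gain g_ik, after subtracting the mastoid average. With no delay, the cross-spectrum of electrodes i and j is Σ_k g_ik g_jk P_k. This is a real number, so the true lag is 0 degrees if it is positive and 180 degrees if it is negative. A rule around 0 addresses only the first case. This needs no head model.

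**2. Scatter of the estimated lag.** The theta band is 4–8 Hz, so a 2 s epoch holds about 4 Hz × 2 s = 8 independent samples. The approximate standard deviation of an estimated phase is √[(1 − γ²)/(2nγ²)]. Take n = 8 and assume coherence γ = 0.5 (in the alpha simulation below, the cut-off for the strongest 15% was 0.48–0.54):

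√[0.75/(2 × 8 × 0.25)] = √0.1875 = 0.433 rad ≈ 25 degrees.

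On a normal approximation, about 69% of purely mixed pairs fall outside ±10 degrees and about 23% outside ±30 degrees.

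If 0 degrees meant within half a sample at 512 Hz, then at 10 Hz the implied tolerance would be ½ × 360 × 10/512 ≈ 3.5 degrees.

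**3. Band power.** For Gaussian band-limited signals, the correlation of power equals |γ|², which does not depend on the angle. If a pair has mixing plus genuine lagged coupling, its angle moves off 0 and it is retained, but |γ|² still contains the mixing part.

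**4. Simulations with zero true coupling.** Independent sources were mixed without delay to 64 electrodes, so every edge is spurious. The first two simulations used a mastoid-average reference and removed neighbours. Of 64 × 63/2 = 2016 pairs, 1837 remained in the alpha simulation. Source number, noise, geometry, neighbour distance and edge density are assumptions, not taken from the plan.

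| Among the strongest pairs | Theta, 40 sources, top 10% | Alpha, 10/30/100 sources, top 15% | Second theta simulation |
|---|---|---|---|
| At exactly 0 degrees | 0% | 0% | 0% |
| Single 2 s epochs: left by a 10-degree tolerance | 100 − 30 = 70% | 67–76% | 100 − 37 = 63% to 100 − 24 = 76% |
| Pooled record: within 10 degrees of 0 | 83% | 83–100% | 97–99% |
| Pooled record: within 10 degrees of 180 | 17% | 0–17% | 1–2% |
| Near 180 after near-0 pairs are dropped and others promoted | 84% | 2–66% | 24–70% |

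The pooled record was 3 minutes in the theta simulations and 60 × 2 s = 2 minutes in the alpha one.

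In the alpha simulation, the share left in single epochs was 97–98% at 1 degree, 83–88% at 5 degrees and 23–47% at 30 degrees. Among non-neighbour pairs, median power correlation was 0.03–0.11, and 4–7% of pairs exceeded 0.3, all without true coupling.

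**5. Effect on modularity (alpha simulation, 15% of pairs kept as edges).**

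| Rule | Network | Mixing only | Degree-matched random graphs |
|---|---|---|---|
| Exact 0 | Phase | 0.20–0.36 | 0.18–0.22 |
| Exact 0 | Power | 0.24–0.33 | 0.20–0.22 |
| 10 degrees, lag over whole record | Phase | 0.20–0.25 | 0.19–0.24 |
| 10 degrees, lag over whole record | Power | 0.20–0.23 | 0.19–0.24 |

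CPL was not simulated. It is computed from the same edges.

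**The case against.** **The exact-0 reading is uncharitable.** No analyst would require an angle to equal 0 to machine precision, and the plan records several minutes of rest. Judged over the whole recording with a 10-degree tolerance, the rule would catch 83–100% of the strongest mixing-only pairs. That is true, and on that reading most of the scatter problem goes away. But neither the tolerance nor the pooling is written, and the plan computes connectivity in two-second epochs. The 180-degree pairs and the power correlations remain under any tolerance around 0.

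**The consequence is not quantified.** This stands. With true coupling set to zero, every edge is spurious by construction, so the simulations cannot give the spurious share in real recordings. Mixing-only modularity overlaps random graphs at the low end under the exact-0 rule, and is close to them once a 10-degree whole-record tolerance is applied. Nothing was tested about whether mixing varies between participants in a way that distorts the Spearman or stepwise analyses.

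**The scope is limited.** This stands too. The plan calls itself a pilot, names the ERP old/new effect as its primary ERP measure, and treats the network metrics as candidate biomarkers.

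**The remedy has a cost.** Imaginary coherency scales with the sine of the lag, so it also shrinks genuine small-lag coupling. That is correct and is counted under the fix.

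A reader might infer that most edges in this trial will be artifact, that 180-degree pairs are the main fault, or that any tolerance around 0 misses most mixed pairs. The plan and the calculations do not support these readings. The 84% figure is the top of a 2–84% range and applies only after near-0 pairs are dropped. Scatter around 0 is usually the larger part of the problem. A 30-degree tolerance removes more than half of the mixed pairs even in single epochs.

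**Conclusion.** The concern holds as a fault in the stated rule, not merely as missing detail. Three failures rest on signal algebra and not on a head model: an exact-0 condition removes essentially nothing, opposite-sign mixing is kept, and lag screening does not clean the power correlations of retained pairs. The percentages do depend on the assumed sources, noise, geometry and edge density, and should be read as ranges.

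Resting-state modularity and CPL can therefore partly reflect mixing. How far they would do so in this trial's data is unknown. Only the resting-state prediction aim is affected. The ERP old/new effect and the neuropsychological outcomes do not use this rule. The change should be made before the network analysis is run, but it does not threaten the trial as a whole.

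**What to change.** Replace the 0-degree exclusion under EEG Time-Frequency and Network Analysis as follows:

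- **Phase network:** use a measure insensitive to lags of both 0 and 180 degrees, such as the weighted phase lag index or imaginary coherency, estimated over all artifact-free epochs together and not per 2 s epoch.
- **Power network:** use envelope correlation after pairwise orthogonalisation.
- Then threshold, binarize and compute modularity and CPL as planned.

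At minimum, exclude pairs within a stated tolerance of both 0 and 180 degrees, judged over the whole recording, and orthogonalise the power envelopes.

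The cost is analysis wording and code on the same recordings. Genuine zero-lag coupling is lost, which the plan already gives up, and some genuine small-lag coupling is lost or down-weighted. The plan's present measures can be kept as a sensitivity analysis to show how much the metrics depend on this choice.
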